## **Study Protocol**

### **"IMPACT OF A PREOPERATIVE OUTPATIENT EDUCATION PROGRAM FOR OSTOMY PATIENTS: A COHORT-COMPARATIVE PILOT STUDY"**

#### **Introduction**

Data reported from Spanish Ostomy Association estimate that 1.5% of total population are living with an ostomy. Colorectal cancer is the most common diagnosis associated with stoma formation (80% of the total cases), followed by inflammatory bowel disease in about eight per cent. Currently there's no doubt about the role of specialized nurse in health education relative to stoma care and adaptation process. Preoperative stoma site marking is widely recommended by the main Scientific Societies related to colorectal and urological cancer. It is one of the most impactful measures provided by stoma care specialist nurses, as patients have less stoma-related complications and higher postoperative health-related quality of life scores.

Stoma creation after colorectal surgery is recognized in some studies as an independent cause of prolonged hospital stay and readmissions. However, other publications have not confirmed this point. Gumbo et al, in a retrospective study, reported no differences in postoperative complications or postoperative stay including readmissions between patients who underwent anterior rectal resection and anastomosis with or without a diverting ileostomy, in the setting of a multidisciplinary team and a multimodal rehabilitation program. Studies suggest that preoperative education and counseling has proven to result in significantly better competence in self-care stoma and enhancement in self-management of complications. Nevertheless, there is a lack of data regarding the optimal timing of planned teaching. Studies developed in other fields like breast cancer surgery, indicate that women

postoperatively experience a decreased ability to direct attention and perform tasks. This is consistent with the study published by Cupples concerning recovery from cardiac surgery, concluding that patients who received education 5 to 14 days preoperatively, a preoperative phone call, as well as postoperative teaching, had higher preoperative knowledge and lower postoperative anxiety states than patients who only received preoperative teaching after admission to the hospital. Additionally, the incorporation of minimally invasive surgery results in shorter hospitalizations and less time gaining proficiency in stoma management.

Up to date, conventional practice in our team involved stoma education being imparted postoperatively. Given that, we questioned if implementing a preoperative program could influence postoperative course in new ostomate patients. The purpose of this study is to evaluate the effectiveness of preoperatively education in the outpatient setting in reducing length of stay for stoma patients, compared to standard postoperative care. Secondary end points will be minor and major morbidity, mortality, reoperation and readmission rates assessment.

### Material and Methods

Consecutive colorectal surgery patients undergoing stoma formation in a single center will be recorded in a cohort study, during a 12-month period. Records will be retrospectively collected before outpatient information program establishment and prospectively in the second study period. Data and personal identities of individual participants are coded to ensure patient confidentiality. Patients in the standard group received stoma education after surgery, during hospital stay, and patients in the intervention group received the same information preoperatively in outpatient setting.

Inclusion criteria considered for scheduled preoperative clinic visit: patients older than 18 years of age undergoing elective colorectal resections that eventually would require formation of a stoma (colorectal cancer up to 20 cm from the anal verge, colonic poliposis and inflammatory bowel disease). Patients will be excluded from the study if they already had a stoma before the operation or in case of emergent surgery.

Patients in the study group have one individual consultation 45 minutes in duration several days before surgery with the stoma nurse specialist, following standard ostomy teaching plans (displayed in Table 1).

1. General information about what is a stoma and different types of stoma
2. Potential surgical procedure
3. Information about stoma marking (benefits and timing to perform)
4. How to care your ostomy
5. Effect of the diet on ostomy management
6. An overview on dietary advice
7. *Types of ostomy bags*
8. Complications that may arise after an incorrect apply of a new pouching system
9. How to manage peristomal skin irritation if necessary
10. Influence of stoma on quality of life
11. *Sports and fitness activities you are able to do with a stoma*
12. How and where get the pouches
13. Who to ask if you are in doubt about any procedure
14. Information for family and caregivers

Table 1. Information for ostomy patients

In both groups and in all cases, the stoma site will be marked the same day of surgery. Patients, except for specific contraindication, follow the Enhanced Recovery Pathways established in our colorectal Unit and approved by Local Quality Committee. All procedures will be performed or supervised by a specialist *colorectal* surgeon. Patients, irrespective of the group, are visited in the ward by the enterostoma therapist one or two days after stoma creation, emphasizing basic skills to optimize the ability to perform independently stoma care.

The discharge and readmission criteria are similar for both treatment groups and followed conventional protocols and care pathways set in our working group.

Data collected included age, gender, American Society of Anesthesiologists (ASA) grade, diagnosis, surgical approach and type of stoma. Measurement variables are complications and mortality rates (assessed by Clavien-Dindo Classification), reinterventions, readmissions within the first 30 days after surgery and length of hospital stay. Similar data will be retrospectively collected for patients prior to the introduction of the preoperative education program.

All statistical analyses are performed using SPSS version 20 (SPSS Inc., Chicago, IL, EE. UU.).

Continuously variables were tested by Students T-test, Mann-Whitney U for numerical variables and Pearson's Two-sided Chi-square Test for dichotomous variables or Fisher test for qualitative variables. An alpha level of .05 was used to determine statistical significance.

The article will be reported in line with the STROCSS criteria.

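### Complications are collected retrospectively in the standard group and prospectively in the intervention group, which leaves the minor-morbidity comparison open to differential ascertainment.

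*Combined protocol and SAP*

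**What the plan says.** The Combined protocol and SAP sets out the two collection modes under Material and Methods: "Records will be retrospectively collected before outpatient information program establishment and prospectively in the second study period". Later in the same section, after the list of variables, it repeats this for the earlier patients: "Similar data will be retrospectively collected for patients prior to the introduction of the preoperative education program". Patients taught after surgery form the standard group and patients taught beforehand in clinic form the intervention group, so group and period are the same split.

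The endpoint concerned is named in the Introduction: "Secondary end points will be minor and major morbidity, mortality, reoperation and readmission rates assessment". The main aim, also in the Introduction, is to judge the programme's effectiveness "in reducing length of stay for stoma patients, compared to standard postoperative care".

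On how complications are measured, Material and Methods gives a grading scale: "Measurement variables are complications and mortality rates (assessed by Clavien-Dindo Classification". It does not name the source document, the assessor, an abstraction form, or the grade that divides minor from major. No masking is described. A 30-day limit stands next to readmissions in the list of variables; whether it also covers complications is unclear. Dichotomous outcomes are to be compared by chi-square or Fisher test at 0.05, with no adjustment.

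**The concern.** Minor complications are the outcome most dependent on someone noticing an event and writing it down. If the two periods differ in how that is done, the difference between groups mixes the programme's effect with the completeness of recording. Adjustment in the analysis could not repair this: all standard-group patients have one mode and all intervention-group patients the other, so there is no overlap from which to estimate the effect of mode. Only a common way of finding and grading events can remove it.

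The direction is not fixed. If retrospective reading misses more minor events, the programme looks worse than it is, and a real reduction could be hidden or harm suggested. If those recording prospectively know the patient has had the programme and record fewer events, or dismiss a minor event as no complication, the programme looks better than it is. In a pilot, either error could misdirect the decision on further study.

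**Working it through.** **No figure to reproduce.** The documents give no sample size, event rate, capture rate or effect size. The check is therefore textual, with an illustration on assumed inputs.

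**Step 1: does mode coincide with group?** Yes. The two statements on collection agree with each other, and group is defined by period.

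**Step 2: does anything in the text equalise how minor events are found?**

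- Single centre, consecutive patients ("Consecutive colorectal surgery patients undergoing stoma formation in a single center will be recorded in a cohort study"): makes the setting alike, but is silent on how complications are ascertained.
- Ward visit ("Patients, irrespective of the group, are visited in the ward by the enterostoma therapist one or two days after stoma creation"): given to both groups, but described as reinforcing self-care skills, not as outcome assessment.
- Discharge and readmission rules ("The discharge and readmission criteria are similar for both treatment groups"): concern care, not recording.
- Clavien-Dindo: grades an event once identified; it does not say how events are identified.
- Similar data for the earlier patients: fixes which variables are collected, not their source or the way they are abstracted.

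These elements narrow the possible gap. None closes it.

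**Step 3: how capture enters the estimate.** Let s1 be the proportion of minor events captured in the prospective (intervention) period and s0 the proportion captured in the retrospective (standard) period. With one event per affected patient and no false recording:

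observed risk ratio = true risk ratio × (s1 / s0)

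This does not depend on event rate or sample size.

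- True ratio 0.80, s0/s1 = 0.80 (for example 0.76/0.95): 0.80 × (0.95/0.76) = 0.80 × 1.25 = 1.00. The benefit disappears.
- No true effect, with the same relative capture reversed (s1/s0 = 0.76/0.95): 1.00 × 0.80 = 0.80. A benefit appears that is not there.

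**Step 4: range with no true effect.** All capture values are assumptions. The better-captured period is set at 0.95. With two minor events per affected patient captured independently, a patient is counted with probability 1 − (1 − s)².

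| Retrospective capture (prospective 0.95) | One event | Two events |
|---|---|---|
| 0.90 | 0.95/0.90 = 1.06 | 0.9975/0.99 = 1.01 |
| 0.80 | 0.95/0.80 = 1.19 | 0.9975/0.96 = 1.04 |
| 0.70 | 0.95/0.70 = 1.36 | 0.9975/0.91 = 1.10 |

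If instead the prospective period is the poorer one, the one-event ratios invert: 0.90/0.95 = 0.95, 0.80/0.95 = 0.84 and 0.70/0.95 = 0.74. With equal capture every ratio is 1.00.

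The formula does not cover shifts across the minor/major boundary. A major event graded as minor would add to the minor count and lower the major count.

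**The case against.** The strongest reply is that no bias is shown. The sentence on collection has one object, records, for both periods, and no study-specific surveillance, questionnaire or follow-up call is described for the second period. On that reading the same chart is simply abstracted later in one group and as it accrues in the other, and collection mode may add nothing. This stands as a possibility, and it is why the size is put at possibly nil. It does not dispose of the point: the plan draws the retrospective/prospective contrast itself and never says that the source and procedure are common.

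The second reply is that the shift may be small beside the noise. Assuming 25 or 50 patients per group and a recorded rate of 28.5% in each (30% × 0.95), the standard error of the log risk ratio is √(2 × 0.715 / (n × 0.285)), or 0.448 and 0.317. The approximate 95% intervals around a ratio of 1 are 0.42 to 2.41 and 0.54 to 1.86, and a shift to 1.06 or 1.19 lies well inside both. This is fair, and it is a reason not to rest the point on false significance. A systematic shift in the estimate nevertheless remains, and it does not shrink as patients are added.

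A third reply is that the bias is harmless because it is conservative. A reader might infer that a favourable minor-morbidity result is safe, since incomplete old charts can only make the programme look worse. The documents do not support this: no masking is described, and under-recording or down-grading in the prospective period would run the other way.

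**Conclusion.** The concern holds in a limited form. Collection mode is stated to differ by group, the two coincide completely, and the unadjusted minor-morbidity comparison is therefore open to differential ascertainment in either direction. The size is unknown and may be nil. The step from a true 0.80 to an observed 1.00 rests on assumed relative capture of 0.80, one event per affected patient and no false recording; with two independently captured events the distortion is much smaller.

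Two stronger conclusions should not be drawn. A reader might infer that the minor-morbidity result is certainly biased; the text leaves open that both periods use the same chart in the same way. A reader might also carry the point over to the main aim; length of stay follows from admission and discharge dates, not from a search for events, and is not affected here. Death, reoperation and readmission are less exposed than minor events. Confounding by calendar time is a separate matter.

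For one secondary endpoint of a self-described pilot, this is a minor-to-moderate point that is cheap to improve.

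**What to change.** Add to Material and Methods text to this effect:

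> For the between-group comparison, complications in both periods will be abstracted from the same routine clinical record, using one form, one Clavien-Dindo cut-off between minor and major, and one time window, applied identically to both groups. Where existing staff allow, grading will be done with the study period masked. Any additional complications captured prospectively will be reported descriptively for the second period only.

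The plan should also state whether the 30-day limit now attached to readmissions covers complications. Naming the source alone is not enough, because form, cut-off and window would still be open; nor is calling the comparison exploratory, which leaves the method unchanged.

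**Cost.** A few sentences, one abstraction form, and a little extra chart abstraction for second-period patients if it is not already planned. No new patients, staff or procedures are needed. Hours cannot be estimated because no sample size is given.

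**Downsides.** Some detail on minor events is lost from the comparison, and residual bias remains if routine charting itself changed between the periods.

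### Enhanced recovery pathway assignment varies between patients but is not recorded, so a difference in its use between the historical and prospective cohorts could bias the length-of-stay comparison unseen

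*Combined protocol and SAP*

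**What the plan says.** The aim, in the Introduction, is to test whether preoperative outpatient education is effective in "reducing length of stay for stoma patients, compared to standard postoperative care". The comparison is before and after: "Records will be retrospectively collected before outpatient information program establishment and prospectively in the second study period".

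Material and Methods describes two elements of background care. On the recovery pathway: "Patients, except for specific contraindication, follow the Enhanced Recovery Pathways established in our colorectal Unit". On marking: "In both groups and in all cases, the stoma site will be marked the same day of surgery". The Introduction reports that with preoperative marking "patients have less stoma-related complications and higher postoperative health-related quality of life scores".

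The baseline items are these: "Data collected included age, gender, American Society of Anesthesiologists (ASA) grade, diagnosis, surgical approach and type of stoma". The outcomes are complications and mortality, then "reinterventions, readmissions within the first 30 days after surgery and length of hospital stay". For the earlier cohort, "Similar data will be retrospectively collected for patients prior to the introduction of the preoperative education program". Neither list mentions pathway assignment or marking. The statistical paragraph names only two-group tests (t, Mann-Whitney, chi-square, Fisher) at an alpha of .05. It names no regression, matching or other adjustment.

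**The concern.** In a before-after design, calendar period and treatment coincide completely. Anything else that changed between the periods and affects stay is attributed to the programme unless it is measured.

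An enhanced recovery pathway is a natural candidate, because it can plausibly act on the main outcome. The protocol itself says that exposure to it is not uniform. It does not say how many patients are excepted, whether that share was the same in both periods, or when the pathway began relative to the historical period.

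If fewer historical patients were on the pathway, the standard group would stay longer for reasons unrelated to the timing of education, and the programme would look better than it is. If more were, a real benefit could be hidden.

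**Working it through.** **What is recorded.** Setting the care statements against the data lists:

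| Background measure | Stated to vary between patients? | In the data lists? | Outcome the documents link it to |
|---|---|---|---|
| Recovery pathway | Yes, by contraindication | No | None quantified |
| Stoma-site marking | No, asserted for all | No | Stoma-related complications, quality of life |

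The pathway is therefore the measure that bears on the stay comparison.

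**Size of a possible bias.** The plan gives no sample size, standard deviation, stay, pathway use or pathway effect, so there is no figure of its own to reproduce. Every input below is an assumption.

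Bias in mean stay = (difference in proportion on pathway) × (extra days off pathway)

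- 80% v 90%, 2 days: 0.10 × 2 = 0.2 days
- 80% v 90%, 4 days: 0.10 × 4 = 0.4 days
- 70% v 90%, 2 days: 0.20 × 2 = 0.4 days
- 70% v 90%, 4 days: 0.20 × 4 = 0.8 days

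The sign depends on which cohort has the lower use. Lower use in the historical cohort favours the programme, and lower use in the prospective cohort counts against it.

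**Effect on the false-positive rate.** Assume that education has no effect. Simulate log-normal stay with median 8 days and log SD 0.5, add the extra days for off-pathway patients, and apply the Mann-Whitney test at 0.05. With 4,000 simulated studies per case, the Monte Carlo standard error near 5% is √(0.05 × 0.95 / 4,000) = 0.3 points. Ranges are across repeated runs:

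| Pathway use | Extra days | 30 per group | 50 per group |
|---|---|---|---|
| 80% v 90% | 2 | 5.3% | 6.0% |
| 80% v 90% | 4 | 6.7% | 8.1% |
| 70% v 90% | 2 | 5.7% to 6.0% | 6.6% to 7.5% |
| 70% v 90% | 4 | 9.7% to 10.8% | 13.8% to 14.6% |

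**Cross-check.** The simulated stay, before the extra days, has mean 8 × e^0.125 = 9.07 days and SD 9.07 × √(e^0.25 − 1) = 4.8 days. A two-sided normal approximation with 50 per group gives these rates:

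- bias 0.2 days: 5.7% at SD 4, 5.3% at SD 6
- bias 0.4 days: 7.9% at SD 4, 6.3% at SD 6

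These agree with the simulation to within about two points. Inflation grows with sample size: at SD 4, a bias of 0.4 days gives 6.4% with 25 per group, 7.9% with 50 and 10.9% with 100.

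**Marking.** No bias in stay is computed, because the documents do not link marking to stay and state that it was done in every patient.

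**The case against.** The strongest reply is that nothing in the documents points to an imbalance. This is one centre with an established pathway approved by its quality committee, a stated study period of 12 months, and discharge criteria described as similar in both groups. If patients leave the pathway only for a contraindication, a 20-point shift would need a change in case mix. ASA grade, diagnosis and surgical approach are collected and would partly reveal that. The data list may also not be exhaustive.

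Most of this stands. It limits the likely size of the problem and means that the listed variables are partial proxies for pathway use. It does not remove the point: the proxies do not show who was on the pathway, no adjusted analysis uses them, and nothing else in the text suggests that assignment is captured.

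A reader might go further and infer that marking was also unequal, because a rule in the future tense cannot govern care already given to the historical cohort. The documents do not support that. Tense is unreliable throughout: the education of the prospective group and the statistical tests are both in the past tense. Marking is asserted outright for both groups, and the Introduction ties it to complications and quality of life, not to stay. What remains is that the assertion about past patients can be checked from their charts. The check is reasonable because the new stoma-nurse visit covers the benefits and timing of marking (Table 1, item 3).

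**Conclusion.** The point holds as a modest, cheap improvement. Pathway use is stated to vary, is not recorded in either cohort, and would not be adjusted for, so a between-period difference could bias the main comparison without anyone being able to tell.

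Under the assumed inputs the bias is 0.2 to 0.8 days in either direction. With 30 or 50 per group, only the most extreme case inflates the false-positive rate clearly (about 10% to 15%). The others stay at about 5% to 8%, and part of the bias could be picked up by the baseline variables already listed. The true size is unknown, and the sample size, which the plan does not state, also affects it.

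It would be wrong to conclude that the cohorts did differ in pathway use, or that any bias must favour the programme. The documents support neither.

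**What to change.** **Pathway**
- For both cohorts, record whether the patient was assigned to the pathway at surgery (yes/no), with the contraindication if not. Use assignment rather than later adherence, which the education might itself influence.
- Show assignment by group in the baseline table, and state when the pathway began relative to the historical period.
- Prespecify a stay comparison adjusted for pathway assignment together with the baseline variables already collected. Recording alone would reveal an imbalance but not correct it.
- Repeat the stay comparison in on-pathway patients as a sensitivity analysis.

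**Marking**
- Record from the chart whether and when the site was marked, and report the observed proportion by group.
- Repeat the complication comparison in marked patients only if that proportion differs between groups. If everyone was marked, it would merely duplicate the main analysis.

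**Cost.** Two items are added from charts that are already being opened, and clinical care does not change. Some historical charts may lack an entry; report these as not recorded and state the limitation. The adjusted model also uses one more covariate in what is likely to be a small data set.

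### The resection performed is not a listed data item and no adjusted analysis is planned, so a systematic shift in operations between the two cohorts would stay in the length-of-stay estimate and be only partly visible

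*Combined protocol and SAP*

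**What the plan says.** All references are to the combined protocol and SAP.

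- **Aim (Introduction).** The study sets out "to evaluate the effectiveness of preoperatively education in the outpatient setting in reducing length of stay for stoma patients". Morbidity, mortality, reoperation and readmission are secondary.
- **Design (Material and Methods).** Patients at one centre "will be recorded in a cohort study, during a 12-month period". The two groups are separated by time: "Records will be retrospectively collected before outpatient information program establishment and prospectively in the second study period".
- **Eligibility (Material and Methods).** Elective colorectal resections that may need a stoma, for "colorectal cancer up to 20 cm from the anal verge, colonic poliposis and inflammatory bowel disease".
- **Variables (Material and Methods).** "Data collected included age, gender, American Society of Anesthesiologists (ASA) grade, diagnosis, surgical approach and type of stoma". For the historical group: "Similar data will be retrospectively collected for patients prior to the introduction of the preoperative education program".
- **Analysis (Material and Methods).** "Continuously variables were tested by Students T-test, Mann-Whitney U for numerical variables and Pearson's Two-sided Chi-square Test for dichotomous variables", with Fisher's test as a further option. "An alpha level of .05 was used to determine statistical significance". No regression, stratification, matching or propensity method is mentioned.

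The operation performed, the height of the tumour and any preoperative radiotherapy or chemotherapy are not listed anywhere. Table 1 does name the likely operation, but as a topic to teach the patient and not as an item to record.

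**The concern.** Different resections can carry different recovery times and complication risks. The protocol's own Introduction reasons this way about surgery: it links minimally invasive operations to shorter stays, and the retrospective study it cites on diverting ileostomy made its comparison within a single type of resection. Here the eligible diseases admit several types, and because the cohorts are sequential, nothing in the design balances them.

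The listed fields narrow down the operation but do not identify it. A cancer patient with an end colostomy may have had an abdominoperineal excision or a Hartmann-type resection. A patient with inflammatory bowel disease and an ileostomy may have had a segmental resection, a colectomy or a proctocolectomy. A cancer patient with a loop ileostomy may have an anastomosis at any of several heights.

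One possible route to a systematic shift lies in the text. The inclusion criteria are framed around the preoperative clinic visit, so prospective patients may be picked up because a stoma was expected. Historical patients are found from records and may include stomas decided on during the operation. The plan does not say that this happens, but nothing in it would let a reader rule it out.

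At stake is the interpretation of the main result. Fewer long-stay operations in the later cohort would look like a benefit of education; more of them would mask one.

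**Working it through.** The plan states no sample size, power, effect size, standard deviation or stay by operation, so there is no figure of its own to reproduce. The check has a textual part and an illustrative part.

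**Which shifts can be seen, and which adjusted for?**

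| Shift in operations between cohorts | Visible in a table of the listed variables? | Removed by the planned tests? |
|---|---|---|
| Changes the mix of diagnoses, approaches or stoma types | Yes, at least in part | No, the tests are unadjusted |
| Occurs within the same diagnosis, approach and stoma type | No | No |

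The first row could be handled with data already listed if an adjusted analysis were added. The second needs the resection field as well.

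**How large could the hidden part be?** Every input here is assumed; none comes from the documents.

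Bias in mean stay = (shift in share of the longer-stay operation, not captured by the listed variables) × (difference in mean stay between operations).

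- 15 points, 2 days: 0.15 × 2 = 0.3 day
- 15 points, 4 days: 0.15 × 4 = 0.6 day
- 20 points, 2 days: 0.20 × 2 = 0.4 day
- 20 points, 4 days: 0.20 × 4 = 0.8 day

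**What would that do to the test?** Assume no true effect of education, 50 patients per cohort, a two-sided 0.05 level and a normal approximation. Then SE = SD × √(2/n), and the chance of a significant result is 1 − Φ(1.96 − bias/SE) + Φ(−1.96 − bias/SE).

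- SD 4 days: SE = 4 × √(2/50) = 0.8. A bias of 0.8 day gives bias/SE = 1.00 and a rate of 17.0%. A bias of 0.3 day gives 0.375 and 6.6%.
- SD 6 days: SE = 6 × √(2/50) = 1.2. A bias of 0.8 day gives 0.667 and 10.2%. A bias of 0.3 day gives 0.25 and 5.7%.

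The nominal rate is 5%.

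**What do the proxies buy?** Suppose the total shift were 20 points and the gap 4 days. If diagnosis, approach and stoma type captured half of the shift and were adjusted for, 0.8 × (1 − 0.5) = 0.4 day would remain; if they captured 80%, 0.8 × (1 − 0.8) = 0.16 day. Under the planned unadjusted tests the full 0.8 day stays in either case.

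These formulas concern differences in means. The plan also names Mann-Whitney, for which the same shift would move the rank comparison but not by an amount expressed in days.

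**The case against.** Four points can fairly be made on the other side.

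**The proxies are real.** A reader might infer that a change in procedure mix could be neither seen nor adjusted for. The documents do not support that. A move between cancer, polyposis and inflammatory bowel disease, or between colostomy and ileostomy, would show in a baseline table and could be partly adjusted for. This stands, and it limits the hidden part of the problem to shifts within the same diagnosis, approach and stoma type.

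**Not listed does not mean not collected.** The list is introduced in a way that need not be exhaustive, and neither surgical approach nor diagnosis is defined; either might be coded finely enough to help. This also stands: the text shows only that the item is not named. If it is already captured, the correction to the data list is a single line.

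**Chance imbalance is not bias.** A reader might add that small cohorts will often differ in operations by luck alone. They may, but that variation is already part of the standard error of an unadjusted two-group test and does not raise its error rate. Only a systematic difference between the periods does so, and the documents report no change in operative practice. The point therefore rests on a possibility that the plan leaves unchecked, not on a shift known to have occurred.

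**Recording alone would change nothing in the test.** This is correct, and it means that the missing adjusted analysis is as much a part of the point as the missing field.

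What survives is that a reader of the eventual report could not tell, from the listed variables, whether the two cohorts had comparable operations.

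**Conclusion.** The concern holds in limited form. The resection performed is not listed for either cohort, the listed variables stand in for it only partly, and the planned analysis adjusts for nothing. A systematic shift in operations would therefore remain in the length-of-stay estimate, and the part of it within the same diagnosis, approach and stoma type would also be invisible.

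The spurious difference of 0.3 to 0.8 day depends wholly on an assumed uncaptured shift of 15 to 20 points and an assumed gap of 2 to 4 days. It shows what such a shift would do; it does not estimate the bias in this study. The documents do not show that the cohorts differ in operations or in which direction any difference would run. This is a worthwhile, inexpensive improvement and not evidence that the comparison is invalid.

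**What to change.** 1. Add the resection performed to the variable list for every patient in both cohorts, coded the same way. Fix a few categories before analysis, for example anterior resection with diverting stoma, abdominoperineal excision, Hartmann-type resection, colectomy or proctocolectomy, and other, with a stated rule for merging small ones. Settling the coding beforehand avoids choosing categories once the results are known.
2. Optionally, add preoperative radiotherapy or chemotherapy as a yes/no item.
3. Define surgical approach, so that it is clear whether it describes access to the abdomen or the operation itself.
4. Tabulate these items by cohort.
5. Alongside the unadjusted test, prespecify one adjusted or stratified comparison of length of stay that uses resection category.

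The cost is some extra chart time, chiefly for the historical cohort. In a 12-month single-centre pilot the categories will have to be coarse, so the adjusted result would reduce bias from the mix of operations without necessarily removing it. Patient care is unaffected.
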